6.3.2 Blinding

The efficacy study will be conducted with a double blind. The subjects, the clinical staff, and the study team will be blinded to study treatment allocation. The pharmacy team at the study site

Abbreviated Title: Anti-malaria MAb in Mali

Version Date: October 13, 2022

where administration is taking place will be unblinded, and they are responsible for maintaining security of study treatment assignments.

Data will remain blinded until the last subject completes the final study visit. Subjects will then be informed about their study treatment assignment.

Unscheduled unblinding, either intentional (e.g., in the case of a medical emergency in a subject) or unintentional, will be handled according to SOPs. Intentional and unintentional unscheduled unblinding will be documented in the appropriate source and/or research record and will include the reason for the unscheduled unblinding, the date it occurred, who approved the unblinding, who was unblinded, who was notified of the unblinding, and the plan for the subject.

The principal investigator will report all cases of intentional and unintentional unscheduled unblinding to the DSMB in writing within 1 business day after site awareness via email to the DSMB mailbox ([contact]) outlining the reason for the unblinding and the date it occurred. The report will also be submitted to the EC. If an SAE has resulted in unblinding, this information will be included in the SAE Report.

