2.2.3 Laboratory Assessments of CIS43LS

Some laboratory assessments in this study are designed to characterize the investigational product. This includes PK analysis and evaluation for anti-drug antibody (ADA) development after product exposure. Other assays may also be completed from stored samples at a later date.

The LIG International Center of Excellence in Research Lab at the USTTB in Bamako will process blood and store coded samples and will either perform sample testing or ship coded samples to designated research laboratories at LIG/NIAID and VRC/NIAID or other approved collaborators. The key to the code will remain at the USTTB. See section 1.3 for schedules, blood volumes, and tube types to be used for research sample collection. Research assays will be performed on samples from both study product recipients and placebo controls at baseline and throughout the study.

Tube types for clinical labs are according to institutional requirements and are shown in section 1.3 to estimate blood volumes. Different tubes for clinical evaluations may be used to meet site requirements. Research sample tube types and blood volumes must be used as shown or

Abbreviated Title: Anti-malaria MAb in Mali

Version Date: October 13, 2022

as otherwise instructed by the manufacturer. In some instances, coded samples may be transported directly by study staff to the laboratory of an approved collaborator.

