8.2.3 Correlative Studies for Research/Pharmacokinetic Studies

The following evaluations will be performed according to the schedule presented in section [1.3](#).

Blood smear: Thick blood smears will be prepared and analyzed by the standard WHO method (section [2.2.3.3](#)) to identify Pf infection for the primary endpoint. This evaluation will be performed centrally in the laboratory in Bamako.

Pf RT-PCR: RT-PCR will be performed to identify Pf infection as a secondary endpoint. This evaluation will be performed at the University of Washington on coded dried blood spots.

PK studies: Blood CIS43LS concentrations will be measured by Meso Scale Discovery LLC-based automation platform. The concentration at the visit prior to the first Pf infection will be used to assess CIS43LS-mediated protection. This evaluation will be performed at the NIAID.

ADA detection: Assays for detection of ADA will be performed at specified timepoints (section [1.3](#)) following product administration and compared to baseline status. This evaluation will be performed at the NIAID.

Parasite genotyping: For subjects who become infected during the study, coded blood samples collected around the time of the first infection will be used to perform a genotypic sieve analysis to analyze sequences of breakthrough parasites (section [9.4.11](#)). This evaluation will be performed by [name] at the Harvard School of Public Health.

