8.4.2.1.2 Causality

Causality (likelihood that the event is caused by the study agents) will be assessed by the principal investigator or designee considering the factors listed under the following categories:

Definitely Related

- reasonable temporal relationship
- follows a known response pattern
- clear evidence to suggest a causal relationship
- there is no alternative etiology

Probably Related

- reasonable temporal relationship
- follows a suspected response pattern (based on similar agents)
- no evidence of a more likely alternative etiology

Possibly Related

- reasonable temporal relationship
- little evidence for a more likely alternative etiology

Unlikely Related

- does not have a reasonable temporal relationship

Abbreviated Title: Anti-malaria MAb in Mali

Version Date: October 13, 2022

AND/OR

- there is good evidence for a more likely alternative etiology

Not Related

- does not have a temporal relationship

AND/OR

- definitely due to an alternative etiology

Note: Other factors (e.g., dechallenge, rechallenge, if applicable) should also be considered for each causality category when appropriate. Causality assessment is based on available information at the time of the assessment of the AE. The investigator may revise the causality assessment as additional information becomes available.

Causality assessment will be reviewed by the sponsor. The sponsor may make a separate and final determination on the “reasonable possibility” that the event was “related” (comprising definitely, probably, and possibly related) or “unrelated” (comprising unlikely and not related) to the study agent, in keeping with applicable (US FDA) guidance on sponsor IND safety reporting.

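### Section 6.3.2 lets the blind end at the last subject's final visit, without waiting for final smear reads, final AE causality or database lock

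*Combined protocol and SAP*

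**What the plan says.** Section 6.3.2 names one event that ends the blind: "Data will remain blinded until the last subject completes the final study visit". The next sentence reads "Subjects will then be informed about their study treatment assignment". The same section lists who is masked: "The subjects, the clinical staff, and the study team will be blinded to study treatment allocation". Laboratory readers are not named separately.

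Several other sections bear on what may still be open at that event:

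- Section 8.2.3, on the thick smears that define the primary endpoint: "This evaluation will be performed centrally in the laboratory in Bamako". On RT-PCR, the secondary endpoint: "This evaluation will be performed at the University of Washington on coded dried blood spots". Neither has a stated completion date.
- Section 8.4.2.1.2, on AE causality: "The investigator may revise the causality assessment as additional information becomes available". The sentence there that begins "The sponsor may make a separate and final determination on the" gives the sponsor the last word on relatedness. Neither step has a cut-off date.
- Section 8.4.2.3.1 lets AE entry run on a two-week cycle that covers data up to one week before entry. Section 8.4.2.3.2 follows unresolved serious AEs past the last visit.
- Section 9.4.5 compares the proportion of subjects with related AEs between the CIS43LS arms and placebo.

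**The concern.** A visit date does not mark the point at which the data are complete. Between the last visit and a clean database, smears have to be read, doubtful reads reconciled, late AEs entered, queries answered and causality signed off. Smear microscopy and causality attribution call for judgement, and the blind exists to protect that judgement. If the code may be opened at the last visit, the plan permits this work to be finished by people who know the allocation.

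What is at stake is the credibility of the related-AE comparison and, to a smaller extent, of the last primary-endpoint reads. The related-AE comparison is the more exposed because it rests directly on a revisable judgement.

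**Working it through.** **1. Is a completeness condition stated anywhere?** Sections 6.3.2, 8, 9 and 10 were read for one. None ties unblinding to completed reads, closed queries or a lock. The only data lock mentioned is that of the phase 1 study (section 2.2.2.1).

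**2. What can be open at the trigger?**

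| Item | What the plan fixes | What stays open |
|---|---|---|
| AE causality | Assessed by the investigator, reviewed by the sponsor | Revisable with no cut-off; feeds the 9.4.5 comparison |
| AE entry | At least every 14 days, data to 7 days before entry | An event can be up to 14 + 7 = 21 days old before it must be in the database, although 8.4.2.2 asks for prompt recording |
| Smears | Read centrally; used for diagnosis during the study | The last subject's day-168 smear is taken at the trigger visit itself, so its read can fall afterwards |
| RT-PCR | Off-site, on coded spots | No completion date, but the assay laboratory works on coded samples |

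**3. How many smears?** The documents give no reading lag. Assume 2 to 4 weeks for reading and queries. For the last subject, 168 − 14 = 154 and 168 − 28 = 140, so at most the last one or two fortnightly visits (days 154 and 168) fall inside the lag. Only late-enrolled subjects are affected. Because the analysis in section 9.4.4 is time to first infection, only those with no earlier positive smear matter.

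**4. RT-PCR count.** Sections 2.2.3.3 and 4.1 start the smear-based endpoint at day 7 (1 week). Using the same window, the scheduled visits are days 7, 14, 21, 28, 42, 56, 70, 84, 98, 112, 126, 140, 154 and 168, which is 14. So 14 × 330 = 4,620 scheduled spots before dropout. How many would be run after the trigger is not stated.

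**5. Scale, as illustration only.** The plan's own figure is reproduced first. Section 9.2.2 gives 80% power with 110 per arm, 10% dropout, placebo infection rate 0.4, efficacy 0.5 and two-sided alpha 0.025.

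- n = 110 × 0.9 = 99 per arm; p = 0.4; q = 0.4 × (1 − 0.5) = 0.2; mean 0.3; z = 2.2414.
- Power = Φ{[(p − q) − z·√(2 × 0.3 × 0.7/99)] / √[(0.4 × 0.6 + 0.2 × 0.8)/99]} = Φ{(0.2 − 2.2414 × 0.0651)/0.0636} = 80.2%. This agrees with the plan.

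Now take no true effect. Assume that a net share m of positive subjects in one CIS43LS arm is re-read as negative, so q = p(1 − m), and apply the same formula. The values of m are assumptions; the documents give none.

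| m | p = 0.4: subjects (99pm), false-claim chance | p = 0.7: subjects, false-claim chance |
|---|---|---|
| 0 | 0, 1.25% | 0, 1.25% |
| 2% | 0.8, 1.7% | 1.4, 2.1% |
| 5% | 2.0, 2.5% | 3.5, 4.3% |
| 10% | 4.0, 4.8% | 6.9, 11.5% |

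The chances are one-sided, from a comparison of proportions. The table shows that a few one-directional reversals would matter. It does not estimate this trial's exposure: it applies m to all positive subjects, and step 3 shows that far fewer reads are open.

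**6. Is the trigger itself clear?** Appendix D also calls the month-12 pregnancy follow-up visit a final study visit. Reading the trigger that way would delay unblinding but would still not tie it to final data.

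**The case against.** The strongest reply is that section 6.3.2 sets an earliest point and an order of events. It does not instruct anyone to open the code that day. No section says that reads or queries will be unfinished then. Smears serve diagnosis during the study and results are shared with subjects (sections 2.2.3.3 and 8.2.1), so most will have been read earlier. Accumulating data are monitored at least weekly (8.4.2.3), serious AEs go to the sponsor's safety office within one to three business days (8.4.2.3.2), and revising causality presupposes new information. The related-AE comparison is an additional analysis, not the primary efficacy endpoint. All of this stands. It limits the size of the point but does not supply the missing condition.

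Three stronger readings are tempting, and the documents do not support them:

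- **The sample code gives smear readers the allocation.** Section 2.2.3 does say "The key to the code will remain at the USTTB", and the same institution's laboratory processes samples. But that key links samples to subjects. The allocation list is held by a designated pharmacist (6.3.1), and no section says that readers have either.
- **Most of the RT-PCR endpoint would be generated unblinded.** This needs the spots to be batched after the last visit, which is stated nowhere. Even then, opening the code does not by itself unmask an outside laboratory working on coded spots.
- **The covariates for the adjusted Cox model should be listed before unblinding as part of this edit.** Section 9.4.4 may add covariates that differ significantly between arms. That selection needs arm labels, so no such list can be fixed blind under the current rule. It is a separate issue that a later unblinding date does not cure.

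**Conclusion.** The point holds as a defect in a stated rule. The plan permits unblinding before the data are final, and nothing elsewhere prevents it. The absence of a completeness condition is certain; the consequence is only possible. By data type, the exposure is clearest for AE causality, limited to a small number of late smears for the primary endpoint, and weak for RT-PCR. The smear statement rests on an assumed lag of 2 to 4 weeks. A reader might infer from the illustrative table that the type I error is materially inflated. The documents do not support that, because they give no misclassification rate and the window of open reads is narrow. The plan's 80% power figure reproduces and is not in question. The change is worth making because it removes an avoidable source of doubt at almost no cost.

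**What to change.** Replace the two sentences in section 6.3.2 with wording such as:

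*Allocation stays blinded until all scheduled and illness-visit smears have been read and reconciled, RT-PCR results for the efficacy endpoint have been received, AE severity and causality are final, queries are closed and the database is locked. Laboratory readers remain masked to arm until then. Subjects are told their assignment after lock.*

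The cost is a short edit to one section, and subjects learn their arm some weeks later. N, alpha, power and unscheduled unblinding for medical need are unchanged. Section 9.4.4 does not need to change for this edit. If the code has already been opened, the sponsor should instead document when smear reads, AE causality and queries became final relative to that date.

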6.4 STUDY INTERVENTION COMPLIANCE

Study intervention administration will be documented by study staff.

6.5 CONCOMITANT THERAPY

All concomitant prescription and nonprescription (including over-the-counter, herbal, or traditional) medications taken during study participation will be recorded. For this protocol, a prescription medication is defined as a medication that can be prescribed only by a properly authorized/licensed clinician.

Treatment with the following drugs and procedures will not be permitted unless discussed with and approved by the investigator:

- Live vaccines within 4 weeks of study agent administration.
- Killed vaccine within 2 weeks of study agent administration.
- Immunoglobulins and/or blood products for the duration of the study.
- Receipt of any investigational product or co-enrollment in other clinical studies of investigational products.
- Oral or IV corticosteroids at immunosuppressive doses (i.e., prednisone >10 mg/day) or immunosuppressive drugs for the duration of the study.
- Antimalarials and antibiotics with known antimalarial activity.

7 STUDY INTERVENTION DISCONTINUATION AND PARTICIPANT DISCONTINUATION/WITHDRAWAL

7.1 DISCONTINUATION OF STUDY INTERVENTION

Study intervention may be discontinued for a protocol-defined group or arm (i.e., pausing), or it may be discontinued for all subjects and enrollment suspended (i.e., halting). Pausing and halting

Abbreviated Title: Anti-malaria MAb in Mali

Version Date: October 13, 2022

are described in sections [8.4.5](#) and [8.4.6](#). Subjects who have already received the study agent at the time of a pause or halt will continue planned follow-up under the protocol.

7.2 PARTICIPANT DISCONTINUATION/WITHDRAWAL FROM THE STUDY

Plans for managing the involuntary withdrawal of a subject are provided in section [8.4.3](#). The reason for subject discontinuation or withdrawal from the study will be recorded on the case report form (CRF).

Subjects who withdraw after receiving study agent but prior to study completion will be encouraged to attend an early termination visit, where they will complete as many of the procedures and evaluations indicated in the schedule of activities (section [1.3](#)) as possible.

7.3 LOST TO FOLLOW-UP

A subject will be considered lost to follow-up if he or she fails to return for 3 consecutive scheduled visits and is unable to be contacted by the study site staff.

The following actions must be taken if a subject fails to return to the clinic for a required study visit:

- The site will attempt to contact the subject and reschedule the missed visit within 7 days, counsel the subject on the importance of maintaining the assigned visit schedule, and ascertain if the subject wishes to and/or should continue in the study.
- Before a subject is deemed lost to follow-up, the investigator or designee will make every effort to regain contact with the subject (where possible, 3 telephone calls). These contact attempts should be documented in the subject's medical record or study file.
- Should the subject continue to be unreachable, he or she will be considered to have withdrawn from the study with a primary reason of lost to follow-up.

8 STUDY ASSESSMENTS AND PROCEDURES

8.1 SCREENING PROCEDURES

Screening will be performed at the Kalifabougou study site. The study staff will explain the study to the prospective subject, complete the study comprehension examination and obtain consent (section [10.1](#)), and assess eligibility. Consent will be obtained before any study-related procedures are performed.

The following screening procedures and evaluations must be performed within -56 to -7 days of study intervention. Screening may take place over multiple visits if necessary.

- Confirmation of identity, age, and residency.
- Complete review of medical history and medication use.
- Complete physical examination, including height and weight.
- Vital signs (temperature, blood pressure, and pulse).
- 12-lead ECG.
- Urine collection for urinalysis (urine dipstick or formal urinalysis; acceptable laboratory parameters defined in [Appendix A](#)).

Abbreviated Title: Anti-malaria MAb in Mali

Version Date: October 13, 2022

- For women, serum β -hCG pregnancy test.
- Blood collection via venipuncture for screening evaluations:
 - HIV tests: 2 rapid diagnostic tests (RDTs), plus ELISA if the RDTs are discordant. A subject will be referred for medical care for 2 positive RDTs or a positive ELISA. If the ELISA is negative, no further work-up will be done. Pre- and post-test HIV counseling will be provided.
 - HBV and HCV tests. If either test is positive, the subject will be referred for care regardless of the ALT result.
 - Hemoglobin typing.
 - Complete blood count (CBC) with differential.
 - ALT.
 - Cr.
- Pregnancy prevention confirmation and counseling.
- Pre- and post-test HIV counseling.

A prospective subject who has any clinically significant abnormal finding and/or is diagnosed with a medical condition at screening or during the conduct of the study will be notified and referred for medical care. Per national requirements for reporting communicable diseases, confirmed positive test results for HIV, HBV, and HCV will be reported to the local health department according to applicable laws and appropriate medical referrals initiated. The cost of initial and long-term treatment and care of medical conditions diagnosed during the screening process will not be reimbursed by the study but referrals to relevant specialist will be provided.

Screening evaluations may be repeated as described in section 5.5, at the discretion of the investigator. If screening is completed outside the specified window, all screening procedures and evaluations must be repeated. If an individual screens and is enrolled into the dose-escalation study but for any reason does not receive study agent, they may later consent to be screened and enrolled in the efficacy study.

Enrollment: If the individual is eligible and agrees to participate, he or she will be scheduled to come for an enrollment visit, as described in section 1.3. Enrollment is defined as the time of artemether-lumefantrine administration; at this time, the subject will be assigned a unique study identification number in the clinical database. A clinician will discuss the target dates and timing of the study agent administration and sample collections before completing an enrollment to help ensure that the subject can comply with the projected schedule. The identification number will link subject samples and data collected throughout the study.

8.2 EFFICACY ASSESSMENTS

8.2.1 Clinical Evaluations

The following clinical evaluations will be performed as efficacy assessments.

Medical History and Medication Review: A complete review of all medical history and medications will be conducted at screening. Subsequent visits will include a targeted review of changes in medical history or medications since the last study visit.

Physical Examination: A complete physical examination (including height and weight) will be done at screening. A targeted physical examination based on signs, reported symptoms, and

Abbreviated Title: Anti-malaria MAb in Mali

Version Date: October 13, 2022

medical history will be conducted at subsequent study visits. Weight will also be recorded on day 0 prior to study agent administration.

Artemether-Lumefantrine: At enrollment, all subjects will be orally administered standard artemether-lumefantrine treatment (4 tablets twice daily for 3 days) to clear any possible Pf blood-stage infection prior to study agent administration.

Randomization Procedures: Randomization for the efficacy study is described in sections [6.3.1](#) and [9.4.1](#).

Study Agent Administration and Monitoring: Study agent infusion and monitoring will be performed according to the assigned arm, as described in section [6.1](#).

Illness Visit: A subject will be instructed to come in for an unscheduled visit if he or she has symptoms of malaria or other symptoms. The subject will be evaluated by the study team and referred for standard care according to local guidelines. At an illness visit, the subject may undergo review of medical history and concomitant medications, a focused physical exam for symptoms of malaria or other diseases, vital sign measurement, and a fingerprick or venipuncture blood collection for blood smear for malaria diagnosis as well as a dried blood spot for Pf RT-PCR for research purposes.

Malaria Diagnosis and Management: If a subject has a malarial infection, we will share these results with the subject and provide standard treatment in accordance with the recommendations of the Mali National Malaria Control Program. According to the national guidelines, asymptomatic malarial infections in adults are not treated. Malaria treatment is given only when symptoms are present along with positive blood smear results. RT-PCR is not commonly used for routine malaria diagnosis.

